7.4. Procedures for Handling Missing, Unused, and Spurious Data

All available safety, PK, pharmacodynamic, and activity data will be included in data listings and tabulations. No imputation of values for missing data will be performed.

7.5. Analysis Schedule

7.5.1. Interim Analysis

The interim analysis with the first 30 evaluable patients will be conducted using a one-sided 95% CI estimate for the response rate. If the lower bound of the 95% CI estimate with the 30 patients is $\geq 29\%$, the SRC may recommend either terminating the study at the interim based on treatment superiority, or continuing the study as planned. If the lower bound is $< 29\%$, various predicted lower bounds of one-sided 95% CIs for the response rate will be constructed to further guide the SRC's recommendation. For example, assuming a true response rate of 44% for the remaining 36 patients, the expected lower bound of one-sided 95% CI with 66 evaluable patients will be calculated. If the expected lower bound is $\geq 29\%$, the SRC may recommend continuing the study as planned. If the expected lower bound with 66 evaluable patients is $< 29\%$, another simulation will be run with 86 evaluable patients. If the resulting lower bound is acceptable (e.g., close to or $\geq 29\%$), the SRC may recommend expanding the sample size by 20 patients. If the resulting lower bound is not acceptable (e.g., $< 29\%$), the SRC may recommend terminating the study for futility. In addition, the expected lower bound of the one-sided 95% CI when the true response rate is equal to the observed value at the interim analysis will be calculated. The resulting scenario will be similar to the previous one: if the expected lower bound is $\geq 29\%$, the SRC may recommend continuing the study as planned, if the lower bound is $< 29\%$, the SRC may recommend expanding the sample size by 20 patients. Additional simulations with other possible response rates (for example, assuming a 40% response rate), with or without adaptation, will also be conducted; the SRC will review all simulation results to make a recommendation at the interim. Furthermore, with the potential

adaptations at the interim, we find via an extensive simulation study the final CI estimate would have the accurate coverage level. Therefore, no statistical penalty or adjustment will be needed for the final inferential statistical procedure for the response rate.

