7. STATISTICAL PROCEDURES

7.1. Sample Size Estimation

Phase 1b (MTD):

Using a 3+3 design, the total number of patients required for the MTD phase will range from 9 to 30.

Phase 2:

The reference response rate is assumed to be 0.29. For a study with a sample size of 66, a one-sided 0.05 level test with power of 80% would be adequate to detect the response rate of 0.29 against 0.44. Assuming a 10% drop out rate, a study of 75 patients would be sufficient. In order to have a robust study, a single interim analysis will be conducted when there are 30 evaluable patients. The SRC will use the totality of information from the interim analysis to recommend whether the study should proceed as planned, be terminated for superiority or futility, or extended to allow for 86 evaluable patients. Assuming a 10% dropout rate, a study with n=95 would be sufficient.

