7.6.7. Efficacy Analysis

Efficacy analysis will be performed on both the ITT Population and EE Population. The ITT Population will include all patients, and the EE Population will include all patients who meet eligibility criteria, receive at least 14 doses of study drug (i.e., ACY-1215, pomalidomide and low-dose dexamethasone), and have at least 1 post-baseline efficacy assessment. The primary analysis will be based on the EE population, and will use the Investigator-assessed response data evaluated according to consensus recommendations based on the IMWG criteria. Response rate will be percent of patients who achieve at least partial response (PR) at the recommended Phase 2 dose. Percent of patients achieving MR or better will also be collected as clinical benefit response. PFS will be defined as the time from first dose of study treatment to the first documentation of PD or death from any cause during study. Overall survival (OS) will be defined as the time from first dose of study treatment to death from any cause. For responders, TTR and response duration will be analyzed. TTR will be defined as the time from first dose of study treatment to the first documentation of response (either PR or CR). DOR will be defined as the time from the first PR or CR to the first documentation of PD or death, whichever occurs earlier.

For data obtained from patients treated at doses of ACY-1215 not selected as the MTD, a case-by-case description of myeloma response (per IMWG criteria) will be provided. For the 12 patients who initiate ACY-1215 at the recommended Phase 2 dose level, response rates together with confidence intervals will be provided. Kaplan-Meier curves will be used to characterize the time-to-event curves (PFS, OS, response duration) when there is censoring; univariate summary statistics will be provided for TTR.

For the Phase 2 segment, a 0.95 confidence interval for the response rate will be constructed for evaluating the efficacy of ACY-1215. Kaplan-Meier curves will be constructed to characterize PFS, OS, and DOR. One sample standard inferences for PFS, OS and DOR will be made accordingly.

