7.6.10. Procedures for Reporting Deviations to Original Statistical Analysis Plan

A formal statistical plan for the analysis and presentation of data from this study will be prepared before database lock. Deviations from the statistical analyses outlined in this protocol

will be indicated in this plan; any further modifications will be noted in the final clinical study report.

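### Using the permitted superiority stop at 30 patients with unadjusted one-sided 95% limits raises type I error to about 6.3%, so the no-penalty statement in 7.5.1 does not hold

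*Combined protocol and SAP*

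**What the plan says.** Section 7.1 sets the Phase 2 design: "The reference response rate is assumed to be 0.29", and with 66 evaluable patients "a one-sided 0.05 level test with power of 80% would be adequate" "to detect the response rate of 0.29 against 0.44". It plans one interim analysis at 30 evaluable patients and a possible extension to 86.

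Section 7.5.1, repeated in the synopsis, uses a one-sided 95% interval at the interim. If its lower bound is at least 29%, "the SRC may recommend either terminating the study at the interim based on treatment superiority, or continuing the study as planned". If not, projected lower bounds at 66 and then 86 patients guide a choice between continuing, adding 20 patients and stopping for futility. On the effect of these adaptations it says "we find via an extensive simulation study the final CI estimate would have the accurate coverage level" and then "Therefore, no statistical penalty or adjustment will be needed for the final inferential statistical procedure for the response rate". The simulation's scenarios, stopping assumptions and interval method are not given.

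Section 7.6.7 says only that "a 0.95 confidence interval for the response rate will be constructed for evaluating the efficacy of ACY-1215", with no method and no side. Section 7.6.10 adds: "A formal statistical plan for the analysis and presentation of data from this study will be prepared before database lock".

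**The concern.** The rule gives the trial two chances to exclude 29% at the same nominal one-sided 5% level, with no alpha spent at the first look. Some trials that cross at 30 by chance would fall back below the bar by 66. Stopping turns those into superiority claims.

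The Phase 2 conclusion is a single-arm comparison with a fixed 29%, so the error rate of that comparison is the main protection against a false positive. A stop on 14 or 15 responders of 30 would be reported with an error rate and coverage that the rule does not deliver. This is a likely path: at the design rate of 44%, the trial crosses at 30 with probability 45%. A statistical plan due only before database lock does not ensure that the interval method is fixed before the interim.

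**Working it through.** **Inputs.** From 7.1: null rate 0.29, alternative 0.44, one-sided 0.05, 66 evaluable patients, interim at 30, extension to 86. From 7.5.1: unadjusted one-sided 95% limit, superiority stop if the limit is at least 29%, projection at a 44% rate in the remaining patients. Assumption: exact (Clopper-Pearson) limits, since no method is named.

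**Step 1: cut-offs.** The smallest count whose lower limit is at least 29%:

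| n | Cut-off | Lower limit at cut-off | Lower limit one below |
|---|---|---|---|
| 30 | 14 | 30.8% | 27.9% |
| 66 | 26 | 29.3% | 27.9% |
| 86 | 33 | 29.6% | 28.5% |

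Wald limits give the same three cut-offs.

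**Step 2: the plan's own figure.** With a fixed 66 patients, P(X ≥ 26) is 0.0450 at 0.29 and 0.810 at 0.44. The stated 80% power at one-sided 5% reproduces.

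**Step 3: a definite version of the interim rule.** The criteria are soft, so I took the mean projected exact limit at a 44% future rate:
- 14 or more of 30: stop for superiority.
- 10 to 13: continue to 66 (projected limit 29.1% at 10, 27.7% at 9).
- 8 or 9: expand to 86 (projected limit 29.2% at 8).
- 7 or fewer: futility (projected limit at 86 is 28.2% at 7, arguably close to 29%).

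**Step 4: type I error at 0.29.** With b(x) the Bin(30, 0.29) probability:

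α = Σ(x ≥ 14) b(x) + Σ(x = 10 to 13) b(x)·P[Bin(36, 0.29) ≥ 26 − x] + Σ(x = 8, 9) b(x)·P[Bin(56, 0.29) ≥ 33 − x]

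The first term alone is 0.0303. The total is 0.0630, so coverage of the one-sided limit at 29% is 93.7%. A 2-million-run simulation gave 0.0629. Expanding at 7 as well gives 0.0635. With no futility stop and no expansion it is 0.0624, so the excess does not come from how the soft criteria are read.

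**Step 5: where the excess arises.** Under the same rule with no superiority stop, the error is 0.0456. Of the 3.03% of null trials that cross at 30, about 43% would still succeed at 66. Stopping adds the remaining 57%: 0.0303 × 0.57 ≈ 0.017, which is the difference 0.0630 − 0.0456. The error passes 5% once the stop is used in (0.05 − 0.0456)/(0.0630 − 0.0456) ≈ 25% of crossings.

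**Step 6: SRC discretion.** I varied the futility cut-off from none to 9 of 30. At each other interim count I took the smaller, then the larger, rejection probability of going to 66 or 86.

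| Superiority stop | α under the Step 3 rule | Range of α | Power at 0.44 | Expected N at 0.44 |
|---|---|---|---|---|
| 14/30 (as written) | 0.0630 | 0.0543–0.0638 | 0.838 | 50.5 |
| 15/30 | 0.0511 | 0.041–0.052 | 0.828 | 55.5 |
| 16/30 | 0.0470 | 0.0356–0.0479 | 0.824 | 59.7 |
| None | 0.0456 | 0.0335–0.0464 | 0.822 | 66.8 |

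**Step 7: other readings of the interval.** Wilson limits (13/30, 26/66, 32/86) give 0.0954, rising to 0.1069 with free choice of 66 or 86 and no futility stop. A two-sided exact final interval (28/66, 34/86) with the 14/30 stop gives an error of 0.0397 but power of 0.722.

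**The case against.** The stop is optional and the SRC weighs all the information before it. If it always continues after crossing, the error is about 4.6% with exact or Wald limits, and the no-penalty statement is defensible. One could also read that statement as covering only trials that reach a final analysis at 66 or 86. Both points are fair, but 7.1 lists termination for superiority among the interim outcomes, and a stated error rate has to hold for the actions the plan permits. The undisclosed simulation may have left the stop out; the documents do not allow that to be checked.

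Section 7.6.1 says hypothesis testing is not intended. Its reason is the dose-finding goal, whereas 7.1 and 7.5.1 set a test level, power and a superiority stop for Phase 2.

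If the final interval is two-sided, error is controlled at 4.0%. That stands, but power then falls to 72% against the planned 80%, so a stated property fails on either reading. Sections 7.1 and 7.5.1 favour the one-sided reading.

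The excess is also modest for an open-label single-arm Phase 2 trial. That bears on priority, not on whether the statement is right.

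**Conclusion.** The concern holds. With the permitted stop used and one-sided 95% exact or Wald limits at every look, type I error at 29% is about 6.3% against a nominal 5%. No futility cut-off up to 9 of 30 and no choice between 66 and 86 brings it below 5.4%. The result depends on two conditions: that the SRC uses the stop in more than about a quarter of crossings (under the Step 3 rule), and that the final interval is one-sided. The futility and expansion options do not cause the excess. This should be corrected before the interim.

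**What to change.** Before the interim analysis:

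1. Name the one-sided exact (Clopper-Pearson) 95% interval for the final analysis, and state in 7.6.7 that it is one-sided.
2. In 7.5.1 and the synopsis, allow a superiority stop at 30 only if the one-sided 99.5% exact lower limit is at least 29%. That means 16 or more of 30: the limit is 29.3% at 16 and 26.5% at 15. A cut at 15 does not secure 5% under every SRC choice.
3. Replace the no-penalty statement in both places with the operating characteristics: error about 4.7% (3.6% to 4.8% over the SRC's choices) and power about 82% at 44%.

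The cost is protocol and SAP wording; the maximum sample size is unchanged. At a true 44%, the chance of an early superiority stop falls from 45% to 20%, and expected size rises from about 50 to 60 evaluable patients.

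Other repairs also control the error. Removing the superiority stop gives 4.6% error and 82% power, with about 67 patients expected at 44%. Keeping 14/30 and requiring 27/66 at the end gives 4.7% on the 66-patient path without expansion, but power falls to 76.5%.

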7.5.2. Final Analysis

A final analysis is planned after all enrolled patients either complete 6 cycles of study treatment, at treatment discontinuation, or withdraw early from the study.

7.5.3. Addendum

An addendum to the final analysis will be prepared when all patients have withdrawn from the study.

7.6. Statistical Methods

7.6.1. General Methods

Statistical analyses will be primarily descriptive in nature, since the goal of the study is to determine the DLT, MTD, and recommended dose of ACY-1215 in combination with pomalidomide and dexamethasone for further investigation. This goal will be achieved by the results of a deterministic algorithm; thus, statistical hypothesis testing is neither intended nor appropriate within this context.

Continuous variables will be summarized using descriptive statistics (n, mean, standard deviation, median, minimum, and maximum). Categorical variables will be summarized showing the number and percentage (n, %) of patients within each classification. Graphical displays will be provided where useful in the interpretation of results.

7.6.2. Disposition of Patients

Patients who are screened for study entry and do not meet the eligibility criteria will be listed. Reasons for study discontinuation after the start of study treatment will be tabulated by dose cohort. Reasons for discontinuation that are the basis for DLT will be categorized in distinction from other reasons for discontinuation.

7.6.3. Demographics and Baseline Characteristics

The baseline (C1D1) characteristics of patients enrolled in each dose cohort, the Phase 1b MTD segment and the Phase 2 segment, will be summarized. An accounting will be made of the study course for all patients who received study drug for each dose cohort and, in particular, the number of patients who died or withdrew during treatment will be specified and reasons for withdrawal categorized. Study drug administration will be summarized for each dose cohort. Information on dose reductions will be summarized.

7.6.4. Extent of Exposure

Descriptive statistics for patients treated in and completing every treatment cycle, including the number of doses missed or held and dose reductions required, will be presented for every treatment cycle. Furthermore, descriptive statistics for the number of doses received, percent of expected dose received, and actual dose received will be summarized by treatment cycle. A tabular summary and listing of drug administration and dose intensity by treatment cycle and a by-patient listing of the date and time of each study drug dose and the dose administered also will be presented.

7.6.5. Concomitant Medications

A tabulation of all concomitant medications will be produced, with concomitant medications coded using the World Health Organization (WHO) drug dictionary. All concomitant medications administered will be tabulated in a data listing.

7.6.6. Safety Analysis

Safety data for the Phase 1b MTD segment will be summarized when all patients have completed the first 28-day cycle (Cycle 1). Safety data for the Phase 2 segment, as well as for patients from the Phase 1b segment who continued treatment following the completion of the first cycle, will be analyzed when all patients have completed 48 weeks of the study or have discontinued from the study.

Safety evaluations will be based on the incidence, intensity, and type of AEs, and changes in the patient's physical examination findings, vital signs, ECG findings, and clinical laboratory results. All patients who received at least one dose of study drug will be included in the safety analysis. Summarization will focus on occurrence rates of: any SAEs; treatment-emergent AEs by system organ class (SOC) and preferred term; discontinuation rates of study therapy due to AE or toxicity based on clinical laboratory assessment and rates of hematologic toxicity. The frequency of DLT by dose cohort also will be summarized.

AEs will be coded using the Medical Dictionary for Regulatory Activities (MedDRA) for purposes of summarization. All AEs occurring on study will be listed in by-patient data listings. Treatment-emergent events will be tabulated, where treatment-emergent is defined as any AE that occurs after administration of the first dose of study drug and through 30 days after the last dose of study drug, any event that is considered drug-related regardless of the start date of the event, or any event that is present at Baseline but worsens in intensity or is subsequently considered drug-related by the Investigator.

Events that are considered related to treatment (possibly or probably drug-related) will also be tabulated; it should be noted, however, that without a control the primary safety conclusions must be based on overall incidence rates, not those considered treatment-related.

A tabulation will also be provided that enumerates AEs by maximum severity.

Deaths, SAEs and AEs resulting in study discontinuation will be tabulated. AEs leading to dose reduction or interruption will also be tabulated.

Change from Baseline in clinical laboratory parameters will be summarized across time on study, and the frequency of clinically significant abnormal laboratory values will be tabulated. Shift tables will be produced for selected laboratory parameters, to include at least hemoglobin, WBC, ANC, ALC, platelet count, AST, ALT, bilirubin, creatinine, ALP, and electrolytes. These tables will summarize by cycle the number of patients with each baseline CTCAE grade and changes to the maximum CTCAE grade in the cycle.

Changes in vital sign parameters (including BP, heart rate, and temperature) will be summarized over time in a similar fashion to laboratory parameters, and any abnormal values will be tabulated. Changes in ECG findings will be presented in data listing format.

ECOG performance status will be summarized for changes from Baseline to treatment discontinuation; ECOG performance status on Day 1 of every treatment cycle will be presented in data listing format.

Additional safety analyses may be determined at any time without prejudice, in order to most clearly enumerate rates of toxicities and to define further the safety profile of ACY-1215.

7.6.7. Efficacy Analysis

Efficacy analysis will be performed on both the ITT Population and EE Population. The ITT Population will include all patients, and the EE Population will include all patients who meet eligibility criteria, receive at least 14 doses of study drug (i.e., ACY-1215, pomalidomide and low-dose dexamethasone), and have at least 1 post-baseline efficacy assessment. The primary analysis will be based on the EE population, and will use the Investigator-assessed response data evaluated according to consensus recommendations based on the IMWG criteria. Response rate will be percent of patients who achieve at least partial response (PR) at the recommended Phase 2 dose. Percent of patients achieving MR or better will also be collected as clinical benefit response. PFS will be defined as the time from first dose of study treatment to the first documentation of PD or death from any cause during study. Overall survival (OS) will be defined as the time from first dose of study treatment to death from any cause. For responders, TTR and response duration will be analyzed. TTR will be defined as the time from first dose of study treatment to the first documentation of response (either PR or CR). DOR will be defined as the time from the first PR or CR to the first documentation of PD or death, whichever occurs earlier.

For data obtained from patients treated at doses of ACY-1215 not selected as the MTD, a case-by-case description of myeloma response (per IMWG criteria) will be provided. For the 12 patients who initiate ACY-1215 at the recommended Phase 2 dose level, response rates together with confidence intervals will be provided. Kaplan-Meier curves will be used to characterize the time-to-event curves (PFS, OS, response duration) when there is censoring; univariate summary statistics will be provided for TTR.

For the Phase 2 segment, a 0.95 confidence interval for the response rate will be constructed for evaluating the efficacy of ACY-1215. Kaplan-Meier curves will be constructed to characterize PFS, OS, and DOR. One sample standard inferences for PFS, OS and DOR will be made accordingly.

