Efficacy analysis will be performed on both the Intent-to-Treat (ITT) Population and Efficacy Evaluable (EE) Population. The ITT Population will include all treated patients, and the EE Population will include all patients who meet eligibility criteria, receive at least 14 doses of study drug (i.e., ACY-1215, pomalidomide and low-dose dexamethasone), and have at least 1 post-baseline efficacy assessment. The primary analysis will be based on the EE population, and will use the Investigator-assessed response data evaluated according to consensus recommendations based on the IMWG criteria. Response rate will be percent of patients who achieve at least partial response (PR) at the recommended Phase 2 dose. Percent of patients achieving MR or better will also be collected as clinical benefit response. PFS will be defined as the time from first dose of study treatment to the first documentation of PD or death from any cause during study. OS will be defined as the time from first dose of study treatment to death from any cause. For responders, TTR and response duration will be analyzed. TTR will be defined as the time from first dose of study treatment to the first documentation of response (either PR or complete response [CR]). DOR

will be defined as the time from the first PR or CR to the first documentation of PD or death, whichever occurs earlier.

For data obtained from patients treated at doses of ACY-1215 not selected as the MTD, a case-by-case description of myeloma response (per IMWG criteria) will be provided. For the 12 patients who initiate ACY-1215 at the recommended Phase 2 dose level, response rates together with CIs will be provided. Kaplan-Meier curves will be used to characterize the time-to-event curves (PFS, OS, response duration) when there is censoring; univariate summary statistics will be provided for TTR.

For the Phase 2 segment, a 0.95 CI for the response rate will be constructed for evaluating the efficacy of ACY-1215. Kaplan-Meier curves will be constructed to characterize PFS, OS, and DOR. One sample standard inferences for PFS, OS, and DOR will be made accordingly.

Pharmacokinetic Analysis

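### The Phase 2 efficacy interval in 7.6.7 has no side, method or 29% criterion: the stated 80% power holds if it is one-sided, but is about 65% to 73% at 66 patients if it is two-sided

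*Combined protocol and SAP*

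**What the plan says.** Four parts of the protocol bear on how the Phase 2 response rate is judged.

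- **7.1 Sample Size Estimation** sets the null value ("The reference response rate is assumed to be 0.29") and the test: "For a study with a sample size of 66, a one-sided 0.05 level test with power of 80% would be adequate to detect" a rate of 44%.
- **7.5.1 Interim Analysis** is explicit about side: "The interim analysis with the first 30 evaluable patients will be conducted using a one-sided 95% CI estimate for the response rate". It compares the lower bound with 29% and predicts one-sided 95% lower bounds at 66 and 86 evaluable patients. It refers to a final interval and a final inferential procedure for the response rate, but defines neither.
- **7.6.7 Efficacy Analysis** describes the final Phase 2 analysis: "For the Phase 2 segment, a 0.95 confidence interval for the response rate will be constructed for evaluating the efficacy of ACY-1215". The Efficacy Analysis part of the synopsis has the same sentence: "For the Phase 2 segment, a 0.95 CI for the response rate will be constructed for evaluating the efficacy of ACY-1215". Neither names a side, a method or a threshold.
- **7.6.1 General Methods** states the study goal as finding the DLT, MTD and recommended dose, and concludes that "statistical hypothesis testing is neither intended nor appropriate within this context". It makes no exception for Phase 2, whose primary objective in 2.1.1 is efficacy by overall response rate.

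**The concern.** The plan writes one-sided where it means one-sided (7.1 and 7.5.1). A reader of 7.6.7 alone would therefore take an unqualified 95% interval to be two-sided. Requiring the lower limit of a two-sided 95% interval to reach 29% is a test at roughly one-sided 2.5%, not the 5% on which 66 patients were chosen.

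Two things are at stake: whether the stated 80% power applies to the criterion actually used, and whether a given responder count has one agreed interpretation. The second matters more than usual here. The study is open-label (5.3.1), the primary endpoint is investigator-assessed (2.2.1), and the committee that receives the interim response data includes the investigators and the sponsor's medical monitor (4.8). A criterion settled late could be settled with the count in view.

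**Working it through.** **Inputs.** From 7.1: null rate p0 = 0.29, alternative p1 = 0.44, one-sided level 0.05, 66 evaluable patients, possible extension to 86. From 7.5.1: interim at 30 evaluable patients. The protocol names no interval method, so I show several.

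**Formulas.** With X ~ Binomial(n, p) and success at r or more responders, size = P(X ≥ r | 0.29) and power = P(X ≥ r | 0.44). Lower limits use a = 0.05 (one-sided 95%) or a = 0.025 (two-sided 95%), with z the matching normal quantile and p̂ = x/n:

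- exact (Clopper-Pearson): the a-quantile of Beta(x, n − x + 1)
- Wald: p̂ − z√(p̂(1 − p̂)/n)
- Wilson: [p̂ + z²/2n − z√(p̂(1 − p̂)/n + z²/4n²)] / (1 + z²/n)

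**Step 1: the plan's own figure.** At n = 66, one-sided 95%, the smallest passing count is 26 by all three methods (exact limit 0.2927). Size is 0.0450 and power 0.8096. The stated 80% reproduces, and 66 is the smallest n with exact power of at least 80%.

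**Step 2: a two-sided 95% interval at the same n.**

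- Exact: 27/66 gives 0.2895, just short of 0.29; 28/66 gives 0.3034. So 28 are needed.
- Wald: 26/66 gives 0.3939 − 1.96 × 0.0601 = 0.276; 27/66 gives 0.4091 − 1.96 × 0.0605 = 0.2905. So 27 are needed.
- Wilson: 26/66 gives 0.285; 27/66 gives 0.2987. So 27 are needed.

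| n | Criterion: lower limit ≥ 29% | Responders needed | Size | Power at 44% |
|---|---|---|---|---|
| 66 | One-sided 95%, exact, Wald or Wilson | 26 | 0.0450 | 0.8096 |
| 66 | Two-sided 95%, Wald or Wilson | 27 | 0.0255 | 0.7345 |
| 66 | Two-sided 95%, exact | 28 | 0.0137 | 0.6470 |
| 86 | One-sided 95%, exact | 33 | 0.0387 | 0.8774 |
| 86 | One-sided 95%, Wilson | 32 | 0.0619 | 0.9166 |
| 86 | Two-sided 95%, exact, Wald or Wilson | 34 | 0.0232 | 0.8270 |

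Exact power at one-sided 2.5% first reaches 80% at n = 83. These figures ignore the interim options.

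**Step 3: results that change meaning.** Counts of 26 or 27 out of 66 pass the one-sided rule and fail the exact two-sided one. At a true rate of 44% their probability is 0.8096 − 0.6470 = 0.163; at 40% it is 0.0996 + 0.0984 = 0.198.

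**Step 4: the interim stop combined with the one-sided final rule.** On the exact one-sided limit, 14/30 gives 0.308 and so permits a superiority stop. Suppose the stop is taken whenever permitted, and the study otherwise runs to 66 with success at 26, without futility stopping or extension. At a true rate of 29%:

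- P(at least 14 of 30) = 0.0303
- P(fewer than 14 of 30, then at least 26 of 66) = Σ over x ≤ 13 of P(X₃₀ = x) × P(X₃₆ ≥ 26 − x) = 0.0321
- Total = 0.0624, against the nominal 0.05

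**The case against.** The strongest reply is that no section says two-sided. Every place that gives Phase 2 inference a side makes it one-sided, and 7.5.1 does so for the predicted end-of-study bound at 66 and 86 patients, against 29%. Read together, 7.1 and 7.5.1 supply the side and the reference value, and power is then 81%. This stands as the likely intent. It does not supply a final rule: 7.5.1 is interim guidance and leaves the final procedure undefined.

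Section 7.6.1 ties its disclaimer to dose finding by a deterministic algorithm, so it reads as leftover Phase 1 text. A reader might infer that it rules out any Phase 2 inference; its own rationale does not support that. Its placement in General Methods still needs correcting.

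Section 7.6.10 promises a formal statistical plan before database lock, which could settle side and method. That lowers the severity but, in an open-label study, leaves the timing problem.

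A reader might also infer that the trial could stop for superiority on a result whose two-sided interval still contains 29%. For 14/30 this depends on the method: the exact two-sided limit is 28.3%, the Wilson limit 30.2%. The stop is also optional. The example is not firm enough to carry the point.

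Finally, the two-sided shortfall is confined to 66 patients. At 86 the power is 82.7%, though the extension is only an option.

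**Conclusion.** The plan does not define the final Phase 2 efficacy criterion. The side, method and link to 29% are missing from 7.6.7 and the synopsis, and 7.6.1 disclaims testing without excepting Phase 2.

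The tempting stronger reading is that the study is underpowered. The documents do not support it: the stated 80% reproduces (81.0%) under the one-sided rule that 7.1 and 7.5.1 imply. The loss to 64.7% (exact) or about 73% (Wilson or Wald) is conditional on a two-sided reading at 66 evaluable patients. What is established is that two plausible readings give opposite conclusions for 26 or 27 responders out of 66 (exact method for the two-sided reading), an outcome with probability about 16% at a true rate of 44%.

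The calculations assume exactly 66 or 86 evaluable patients and binomial responses. This should be fixed before the results are known; it is a drafting defect, not a design failure.

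**What to change.** 1. In 7.6.7 and the synopsis, state that Phase 2 efficacy is judged by whether the exact (Clopper-Pearson) one-sided 95% lower confidence limit for the response rate is at least 29%. That means 26/66 or 33/86; for any other evaluable number, apply the same limit to the actual n. Report a two-sided 95% interval for description only. Naming the method matters: at 86 patients a one-sided Wilson limit would pass 32 responders, with size 0.0619.
2. In 7.6.1, limit the no-testing sentence to Phase 1b.
3. In 7.5.1, state that if the optional superiority stop (14/30) is used with this final rule and no adjustment, the overall one-sided error is about 6.2%, not 5%.
4. If a two-sided 95% interval is the intended criterion instead, restate the power in 7.1 as about 65% (exact) at 66 evaluable patients.

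The cost is wording in four places. No patients, visits or data are added.
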